**1245.110 (EMPEROR-Preserved) and 1245.121 (EMPEROR-Reduced), both ongoing**

**Aim:** To investigate the safety and efficacy of empagliflozin versus placebo on top of guideline-directed medical therapy in patients with heart failure with reduced or preserved ejection fraction

**Population:** T2D and non-T2D, age ≥18 years, chronic HF (NYHA II–IV)

Figure 9.1: 1 Design of studies 1245.25, 1245.110, and 1245.121

QD/qd, once daily; T2DM, type 2 diabetes mellitus; LVEF, left ventricular ejection fraction; SoC, standard of care

\* Guideline-directed therapies

This meta-analysis will be exploratory. All analyses will be based on the treated set, which includes all patients treated with at least 1 dose of study medication (as randomised). Due to the different patient eligibility criteria (see [Section 9.2.2](#)) and methods in capturing LLA and related events (see [Section 9.3.2.1](#)), two analysis groupings will be used in the meta-analysis. SAF-M1 includes all 3 studies while SAF-M2 includes studies 1245.110 and 1245.121. All

analyses will be carried out separately for each SAF and for each study, unless otherwise indicated in [Section 9.7.1](#) and [9.7.2](#).

The primary outcomes are LLA events (see [Section 9.3.2.1](#)).

LLA events will be analysed using frequency analyses, incidence rates, Kaplan-Meier estimates, and Cox proportional hazards models to compare empagliflozin with placebo. For SAF-M2, where additional information on LLA events are collected on the eCRF, the reasons leading to LLA, the number of LLA episodes, level of LLA, etc., will be summarised.

As the primary analysis, the “on-treatment” approach will include events with an onset date within the treatment period (from first to last dose of study medication plus 7 days to account for the residual drug effect). An ITT approach will be used as a secondary analysis, which includes all events during the observation period after starting randomised treatment, regardless if the patient was taking study medication or not when the event occurred.

Since deaths are competing events to amputations, a competing risk analysis considering all-cause death and a cumulative incidence analysis will be carried out.

Subgroups by demographics, baseline medical conditions, and baseline therapies will be analysed for LLA events for SAF-M1 and SAF-M2 (see [Section 9.3.3](#) for subgroup variables).

The secondary outcomes are AEs related to amputation (see [Section 9.3.2.2](#)).

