## **9.9 LIMITATIONS OF THE RESEARCH METHODS**

This will be a meta-analysis of 3 studies with heterogeneous patient populations. Patients with type 2 diabetes mellitus and increased cardiovascular risk (1245.25) will be pooled together with patients with chronic heart failure with preserved (1245.110) or reduced (1245.121) ejection fraction (see [Section 9.2.2](#) for more detailed eligibility criteria) in SAF-M1. In general, some heterogeneity between the studies can be expected due to the different populations involved in the trials to be pooled. The degree of heterogeneity of the treatment effect between studies will be assessed statistically and clinically/visually. For time-to-event outcomes, visual inspection of heterogeneity includes a forest plot of the individual study hazard ratios, alongside the corresponding estimate from the individual patient data meta-analysis in SAF-M1 and SAF-M2. For statistical assessment of heterogeneity, a Cox model will be provided including in addition the treatment-by-study interaction term. The p-value of

the interaction term from the Cox model in SAF-M1 and SAF-M2 will be used as a statistical measure for heterogeneity. For binary outcomes (frequencies and incidence rates of LLAs and AEs related to amputation), visual inspection of heterogeneity will be performed using forest plots. These will display the frequencies/incidence rates per treatment arm within each study, alongside the corresponding estimate from the pooled analysis in SAF-M1 and SAF-M2. For statistical assessment of heterogeneity,  $I^2$  will be calculated for the relative risk of an LLA or AEs related to amputation. If heterogeneity between studies is present, potential sources of variability will be assessed clinically and conclusions outlined in the final report.

The Cox model is based on the proportional hazards assumption. The proportional hazards assumption will be explored by plotting  $\log(-\log(\text{survival function}))$  against the  $\log$  of time by treatment group and checked for parallelism. The interaction of treatment with  $\log$  of time will be included in the model described above for an exploratory analysis. Further, Schoenfeld residuals for each covariate and treatment will be plotted against time and  $\log(\text{time})$ . If the proportional hazards assumption cannot be verified, potential sources will be assessed clinically and conclusions outlined in the final report.

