In addition as graphical display a cumulative incidence analysis for amputations and competing event of death will be performed.

The competing risk analysis will be performed according to the standard time to event analysis with censoring at the date of last study medication + 7 days and as additional secondary analysis censored at the date of last follow up.

Trial heterogeneity

In general, some heterogeneity between the studies can be expected due to the different populations involved in the trials to be pooled.

The degree of heterogeneity of the treatment effect between studies will be assessed statistically and clinically/visually.

For time-to-event outcomes, visual inspection of heterogeneity includes a forest plot of the individual study hazard ratios, alongside the corresponding estimate from the individual patient data meta-analysis in SAF-M1 and SAF-M2. For statistical assessment of heterogeneity, a Cox model will be provided including in addition the treatment-by-study interaction term. The p-value of the interaction term from the Cox model in SAF-M1 and SAF-M2 will be used as a statistical measure for heterogeneity.

For binary outcomes (frequencies and incidence rates of LLAs and AEs related to amputation), visual inspection of heterogeneity will be performed using forest plots. These will display the frequencies/incidence rates per treatment arm within each study, alongside the corresponding estimate from the pooled analysis in SAF-M1 and SAF-M2. For statistical assessment of heterogeneity, I^2 will be calculated for the relative risk of an LLA or AEs related to amputation.

If heterogeneity between studies is present, potential sources of variability will be assessed clinically and conclusions outlined in the final report.

Sensitivity analysis for missing dates

For LLA a sensitivity analysis will be conducted for incidence rate calculation in SAF-M1 and SAF-M2 excluding all patients with amputations with missing onset dates. This analysis will only be performed if >10% of onset dates are missing.

Overview of performed analyses

Due to the different study designs not all analyses will be performed for each of the 2 pools. The following table indicates which safety analyses will be performed for which pool and the individually studies.

Table 4.3: 1

Overview of analyses that will be performed for the different study poolings and for the individual study

	Poolings and individual study

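### The degree of heterogeneity in hazard ratios is to be measured by an interaction p-value, with no ratio of hazard ratios and interval for 1245.25 against the two heart failure trials

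*SAP*

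**What the plan says.** SAP 4.3, under Trial heterogeneity, sets the aim: "The degree of heterogeneity of the treatment effect between studies will be assessed statistically and clinically/visually". For time-to-event outcomes the visual part is a forest plot: "visual inspection of heterogeneity includes a forest plot of the individual study hazard ratios" is what it says, with the pooled estimate alongside. For the statistical part, "a Cox model will be provided including in addition the treatment-by-study interaction term", and then "The p-value of the interaction term from the Cox model in SAF-M1 and SAF-M2 will be used as a statistical measure for heterogeneity". Protocol 9.9 has the same text. For binary outcomes, I-squared "will be calculated for the relative risk of an LLA or AEs related to amputation".

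The consequence is stated once: "If heterogeneity between studies is present, potential sources of variability will be assessed clinically and conclusions outlined in the final report". Neither document gives a significance level, says what counts as present, or plans an estimate and interval for the difference between trials.

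On why pooling is done at two levels, Protocol 9.1 says that "two analysis groupings will be used in the meta-analysis" and gives two reasons: different eligibility criteria and different capture of amputations. SAP 3.1.2 names treatment groups and capture. Capture is where 1245.25 stands apart. Protocol 9.3.2.1 describes a retrospective search there and dedicated eCRF pages in both heart failure trials.

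**The concern.** The stated aim is a degree, but the only statistical measure for hazard ratios is a p-value. A p-value mixes the size of a difference with the amount of data. With a rare outcome it can be large when the trials differ a good deal, and with a frequent one it can be small when they hardly differ.

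The test is also not focused. Treatment-by-study over three trials has 2 df in SAF-M1. One of them goes to 1245.110 versus 1245.121, which SAF-M2 tests anyway. The difference in capture points to 1245.25 versus the other two, and that is a single contrast.

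At stake is how the SAF-M1 hazard ratio can be read. If the interaction is non-significant, the report as planned has no figure showing how large a difference between the diabetes trial and the heart failure trials remains compatible with the data.

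**Working it through.** The plan states no power, event target or detectable difference for this test, so there is no figure of its own to reproduce.

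**Inputs from the documents**
- Allocation (Protocol 9.5): 1245.25 has 2345 + 2342 = 4687 on empagliflozin and 2333 on placebo, about 2:1. The heart failure trials are 1:1.
- Sizes (Protocol 9.5): 7020, about 4126 and about 2850. The two heart failure trials together have about 6976.

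**Assumptions**
- First-amputation counts for 1245.25/1245.110/1245.121: 90/25/15, 110/40/25 and 130/60/40. That is 1.3–1.9% of 7020 and 0.6–1.4% of 6976.
- The hazard ratio is the same in both heart failure trials and differs from that in 1245.25 by a factor of 1.97. This is only a yardstick: 1.97 is the canagliflozin-versus-placebo hazard ratio in Protocol 7, not a difference between trials.
- Two-sided alpha 0.05, since none is stated.

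**Formulas**
- Information on log HR: w = events × 2/9 for 2:1 and w = events/4 for 1:1.
- Variance of the log ratio of HRs: V = 1/w(1245.25) + 1/w(HF), where w(HF) is the sum over the heart failure trials.
- Noncentrality: (ln 1.97)²/V = 0.4597/V, the same for both tests under this pattern. Power is the upper tail of the noncentral chi-square above 5.991 (2 df) or 3.841 (1 df).
- 95% CI factor: exp(1.96 × √V).

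| Counts | w(1245.25) | w(HF) | V | Noncentrality | Power, 2 df | Power, 1 df | CI factor |
|---|---|---|---|---|---|---|---|
| 90/25/15 | 20.0 | 10.0 | 0.150 | 3.06 | 33% | 42% | 2.1 |
| 110/40/25 | 24.4 | 16.25 | 0.102 | 4.49 | 46% | 56% | 1.9 |
| 130/60/40 | 28.9 | 25.0 | 0.0746 | 6.16 | 60% | 70% | 1.7 |

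At alpha 0.10 the 2-df power is 45%, 59% and 71%.

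**Share of the pooled estimate.** 1245.25 supplies w(1245.25)/(w(1245.25) + w(HF)) = 67%, 60% and 54% of the information in the SAF-M1 log HR.

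**A wider range.** For HR 1 in 1245.25 and 2 in both heart failure trials, using the expected share of events on empagliflozin, 2-df power runs from 0.18 (50 events in 1245.25, 20 in the heart failure trials) through 0.51 (130/75) to 0.78 (200/150). With equal events on the two sides, 80% power needs about 362 events in total with 2 df and 296 with 1 df. Simulation of a likelihood-ratio test agreed within about 2 points where it was run.

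**What the interval adds.** Take 110/40/25, an observed 1.8-fold difference and equal HRs in the heart failure trials. The statistic is (ln 1.8)²/0.1024 = 3.37, so the 2-df p-value is exp(−3.37/2) = 0.19. The ratio of HRs is 1.8 with 95% CI 1.8/1.87 to 1.8 × 1.87, about 0.96 to 3.4. The p-value alone does not show that a threefold difference is still open.

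**I-squared.** I² = max(0, (Q − df)/Q), so it exceeds 50% when Q > 2 df. With no heterogeneity this happens in 14% of cases with three trials and 16% with two. In SAF-M2 with a true 1.97-fold difference, I² is 0% (Q < 1) in 46%, 36% and 25% of cases. This treats the log relative risk as having about the same variance as the log HR.

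**Related adverse events.** With 500 events in 1245.25 and 400 in the heart failure trials (assumed), 2-df power for a twofold difference is above 0.99.

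**The case against.** The plan does not rest on the p-value alone. It calls it one statistical measure, adds forest plots, clinical review and I-squared, and says from the start that some heterogeneity is to be expected. Protocol 9.9 admits that there are only three studies and that they were not powered for amputations. Hazard ratios with 95% CIs are planned for SAF-M1, SAF-M2 and each study (Protocol 9.7.1; SAP 4.3 and Table 4.3: 1), so a reader could approximate the missing contrast by subtracting the 1245.25 and SAF-M2 log hazard ratios. Subgroup interactions by heart failure at baseline and by diabetes come close to it, subject to the 14-event rule. The 2-df test is the usual global test and keeps power for other patterns. The 1-df contrast gains only about 9–10 points in the scenarios tabulated; the real limit is the number of events.

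All of that stands. It reduces the point to a missing estimate and a missing statement of how to read it. It does not remove the point: none of the planned outputs gives an interval for the difference, and comparing separate confidence intervals by eye is a poor substitute.

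A reader might go further and infer that p > 0.05 will be taken as homogeneity and the SAF-M1 hazard ratio then applied to both populations. No section says so, and the primary objective names both pools and each study together.

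**Conclusion.** The point holds as a cheap improvement. For hazard ratios, the degree of heterogeneity has no measure of size, and the global test is not aimed at the contrast in capture that partly motivates the two groupings. Under the assumed counts, a 1.97-fold difference would be detected with 33–60% power by the planned test and 42–70% by the 1-df contrast. The ratio of hazard ratios would be known to within a factor of about 1.7 to 2.1 either way. A non-significant interaction for amputations would therefore be weak evidence of similarity.

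The size rests on event counts, an alpha and a pattern of hazard ratios that the documents do not give. It is tempting to say that the test usually misses a twofold difference. That is not supported: it is so with few heart failure events, but the third scenario above has 60% power, and at 200/150 events power for a twofold difference is 0.78. Nor does it carry over to amputation-related adverse events if those are frequent.

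**What to change.** In SAP 4.3 (Trial heterogeneity) and Protocol 9.9:

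1. Keep the treatment-by-study interaction test. In SAF-M1 add a 1-df term for treatment by (1245.25 versus heart failure trials), with study kept as a factor, and report it as a ratio of hazard ratios with 95% CI.
2. In SAF-M2 report the ratio of hazard ratios for 1245.121 versus 1245.110 with 95% CI.
3. Base the heterogeneity statement on these intervals, and state that p > 0.05 or an I-squared of 0% does not establish homogeneity.

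Do not attach a cut-off of 1.97 to the interval. That figure is a drug-versus-placebo hazard ratio. A rule that sets the pooled result aside whenever the interval contains 1.97 or its inverse would fire in about 100%, 87% and 60% of cases with no heterogeneity at all under the three sets of counts. It would also stay silent once the estimated ratio exceeded about 4.2, 3.7 or 3.4 (1.97 times the CI factor).

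The cost is one extra estimate per pool and a few sentences, with no new data. The downside is that the interval for amputations will probably be visibly wide.

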4.3.1 Disposition, demographic data and baseline characteristics

Patient disposition, demographic data and baseline characteristics will be analysed by means of descriptive statistical measures for each study grouping. The demographic and baseline

efficacy variables along with their categories for demographic and baseline characteristics are defined in the following table.

Table 4.3: 2 Demographic and baseline variables with categories

Variable	Demographics/Baseline characteristics Categories
Sex	Male Female
Race	White Black/African Asian Hawaiian/Pacific Islander Amer. Ind./ Alaska Nat.
Ethnicity	Hispanic/Latino Not Hispanic/Latino
Geographical region ^{&}	Europe Africa/Middle East North America Latin America Asia Other (if any)
Age (years) categories	Version 1 < 65 65 to < 75 75 to < 85 >= 85
	Version 2 < 65 65 to < 75 >= 75
	(Decision will be taken on which version to use based on the size of the elderly population group >=85 years of age)

Variable	Demographics/Baseline characteristics	
	Categories	
BMI (kg/m ²)	<25	
	25 to <30	
	30 to <35	
	≥35	
Weight (kg)	≤70	
	>70 to ≤80	
	>80 to ≤90	
	>90	
Smoking status	Never smoked	
	Ex-smoker	
	Currently smokes	
Time since diagnosis of diabetes	Version 1 for SAF-M1 pool: ≤ 1 year	
	>1 year to 5 years	
	>5 years to 10 years	
	>10 years	
	Not applicable (as no diabetes diagnosed)	
	Version 2 for SAF-M2 pool: ≤ 1 year	
	>1 year to 5 years	
	>5 years to 10 years	
	>10 years to 20 years	
	>20 years	
	Not applicable (as no diabetes diagnosed)	
Baseline HbA _{1c} (%)	Version 1	Version 2
	<8.5	<8
	≥8.5	8 to <9
	(for diabetic patients only)	
Blood pressure (mmHg)	≥ 130/80	
	< 130/80 (controlled)*	
Renal function (eGFR) (CKD-Epi) (mL/min/1.73m ²)	<30	
	30 to < 45	
	45 to <60	
	60 to <90	
	≥90	
Insulin use	Yes/No	
Metformin use	Yes/No	
SU use	Yes/No	

Variable	Demographics/Baseline characteristics Categories
Loop diuretics	Yes/No
Diuretics	Yes/No
Anticoagulant use	Yes/No
Anti-platelet use	Yes/No
Hypertension	Yes/No
Diabetes	T1DM T2DM No Diabetes
Peripheral arterial occlusive disease	Yes/No
Diabetic foot at baseline	Yes/No
Coronary artery disease	Yes/No
Diabetic neuropathy	Yes/No
Diabetic retinopathy	Yes/No
History of lower limb amputation	Yes/No
Osteomyelitis	Yes/No
Gangrene	Yes/No
Nephropathy	Yes/No
Heart failure at baseline	Yes/No

* Patients must have both SBP below 130 and DBP below 80 to be considered controlled.
& Australia included in North America and South Africa included in Africa/Middle East.

4.3.1.1 Disposition

The disposition tables will be based on the treated set. Percentages of patients who prematurely discontinued study medication will be based on the number of treated patients. In addition, a table summarising the number of patients with diabetes and by type of diabetes (T1DM/T2DM) will be produced by treatment group, overall and by study.

The disposition will show the randomized and completed subjects, subjects who withdraw after randomisation and categorised reason for withdrawal. The disposition tables will include these numbers in the pooled sets as well as by individual study.

4.3.1.2 Demographics

The demographic tables will be based on the TS.

4.3.1.3 Baseline characteristics

The baseline characteristics tables will be based on the TS.

4.3.1.4 Concomitant and anti-diabetic therapy

Only descriptive statistics are planned using the TS. Concomitant medication use will be summarised by Anatomical-Therapeutic-Chemical classification 3 (ATC3) and preferred name. Summaries will be presented for concomitant therapies taken at baseline and those initiated on randomised treatment. Separate summaries of drugs used in diabetes at enrolment, use of antihypertensive, ASA or lipid lowering drugs at enrolment by preferred name will be presented. Tables will be provided for each defined SAF grouping.

4.3.1.5 Concomitant diagnoses and diabetic history

Concomitant diseases will be summarised by system organ class and preferred term. Relevant diabetic medical history by treatment group will also be presented. Both summaries will be presented using the TS. Tables will be provided for each defined SAF grouping.

4.3.2 Safety Analyses

All safety analyses will be performed on the TS.

4.3.2.1 Extent of exposure

Extent of exposure will be calculated as the difference between the date of last intake of study drug and the date of the first administration of the study drug plus one day. A descriptive statistics table with mean, SD, median and range of the number of days a patient was on treatment will be provided.

For the secondary ITT approach time in study will be calculated as the difference between the date of last follow up and the date of the first administration of the study drug plus one day. A descriptive statistics table with mean, SD, median and range of the number of days a patient was in the study will be provided. The calculations will be based on the TS, so treatment switches within a study or periods off treatment will not influence the extent of exposure calculation.

The extent of exposure table as well as the table of time in study will also provide a frequency analysis of number and percent of patients belonging to the following categories of exposure/ time in study ranges:

0 to 12 weeks, >12 to 26 weeks, >26 to 52 weeks, >52 to 78 weeks, >78 to 104 weeks, >104 to 156 weeks, >156 weeks.

The number of patient years of exposure/ time in study, calculated as the sum of days over all patients per treatment group divided by 365.25, will also be given per treatment.

4.3.2.2 Adverse Events

All analyses of AEs will be based on the number of patients with AEs (not the number of AEs). For this purpose, AE data will be combined in a 2-step procedure into AE records.

Processing of individual AE information

In a first step, AE occurrences, i.e. AE entries on the CRF, will be collapsed into AE episodes provided that all of the following applies:

- The same MedDRA lowest level term was reported for the occurrences
- The occurrences were time-overlapping or time-adjacent (time-adjacency of 2 occurrences is given if the second occurrence started on the same day or on the day after the end of the first occurrence.
- Treatment did not change between the onset of the occurrences or treatment changed between the onset of the occurrences, but no deterioration was observed for the later occurrence

In a second step, AE episodes will be condensed into AE records provided that the episodes were reported with the same term on the respective MedDRA level and that the episodes are assigned to the same treatment. Internal BI guidelines will be followed for the handling of AE data. Frequency tables of patients with AEs by system organ class (SOC) and preferred terms will be provided and sorted by frequency (within system organ class).

Assignment of AEs to treatment

The primary analysis, the “on-treatment” approach for the analysis of AEs, will be based on the concept of treatment emergent AEs. That means that all AEs with an onset date between first drug intake (post run-in) until 7 days after last drug intake (or time to last follow-up for analyses up to last follow-up) will be assigned to the randomized study drug (1245.25)/first study drug taken (1245.110, 1245.121)).

An ITT approach will be used as secondary analysis. All AEs with an onset date between first drug intake (post run-in) until time to last follow-up will be assigned to the randomized study drug (1245.25)/first study drug taken (1245.110, 1245.121)).

